Study 1368.15, a randomised placebo controlled study investigated the safety, tolerability, pharmacokinetics, pharmacogenomics and efficacy of 2 intravenous doses of BI 655130 in 59 patients with palmoplantar pustulosis psoriasis. Patients were randomized in a 1:1:1 allocation ratio and received either 900 mg BI 655130, 300 mg BI 655130 or placebo intravenously every 4 weeks over a period of 12 weeks. The proportion of patients who achieved ppPASI50 at Week 16 in the total population was similar in all treatment groups (6 of 19 in 900 mg BI 655130 arm, 6 of 19 in 300 mg BI 655130 arm, and 5 of 21 in placebo arm). However, post-hoc subgroup analyses indicated efficacy of both doses of BI 655130 in patients with more severe PPP disease at baseline (above the median PPPASI value of 16.7). In particular, the results on pustule severity were pronounced with a rapid reduction in pustule severity with evidence of a dose response relationship.

In total, 85.7% in the placebo arm and 89.5% in each of the BI 655130 arms (300 mg and 900 mg) reported at least 1 AE while on treatment. There were 3 AEs leading to discontinuation of trial drug in the placebo arm (14.3%), whereas 1 patient in the 300 mg dosing arm (5.3%) and 3 patients in the 900 mg dosing arm (15.8%) discontinued trial medication due to an adverse event. The most frequently reported treatment-emergent AE were nasopharyngitis (placebo 38.1%, 300 mg BI 655130 26.3%, 900 mg BI 655130 42.1%) and headache (placebo 33.3%, 300 mg BI 655130 21.1%, 900 mg BI 655130 31.6%).

PK data indicate target-mediated drug disposition (TMDD) of BI 655130. The saturation of the non-linear elimination pathway is likely occurring after 0.3 mg/kg and BI655130 exhibits linear kinetics at dose-level greater than 0.3 mg/kg. The half-life of BI655130 is approximately 4 weeks in the linear dose range and thus similar to other IgG1 molecules.

In one patient an infusion related reaction was reported. The patient felt “heat” after the infusion of the trial medication during Visit 3. The event was not accompanied by other symptoms, in particular vital signs remained stable. The patient recovered without treatment. There were no clinically relevant abnormalities on treatment with BI 655130 with respect to safety laboratory and vital signs.

Summary

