3.3.4.1 Discontinuation of trial treatment

An individual patient will discontinue trial treatment if:

- The patient wants to discontinue trial treatment, without the need to justify the decision.
- The patient has repeatedly shown to be non-compliant with important trial procedures and, in the opinion of both, the investigator and sponsor representative, is not willing or able to adhere to the trial requirements in the future.
- The patient needs to take concomitant medication that interferes with the investigational medicinal product or other trial treatment, please see Section [4.2.3](#).
- The patient can no longer receive trial treatment for medical reasons (such as surgery, adverse events, other diseases, or pregnancy).

- For individual stopping rules related to specific adverse events, please see Section [4.2](#).

In case of a temporary discontinuation of trial treatment, trial treatment should be restarted as soon as medically justified, please see Section [4.1.4](#), [4.2.2](#). Even if the trial treatment is discontinued, the patient remains in the trial and, given his/her agreement, will undergo the procedures for early treatment discontinuation and follow up as outlined in the [Flow Chart](#) and Section [6.2.3](#).

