6.2.3 Trial Completion and End of Residual Period

For all randomized patients termination of trial medication and trial completion must be recorded on the corresponding eCRF.

For the comprehensive list of the trial procedures required following the end of treatment, please refer to [Flow Chart](#).

Trial Completion:

Trial completion is defined as a patient having reached the EoS visit within the specified window per protocol.

Treatment Completion:

Treatment completion is defined as a patient receiving four (4) infusions of trial drug (BI 655130 or placebo) at V2, V4, V5 and V6.

Proprietary confidential information © 2020 Boehringer Ingelheim International GmbH or one or more of its affiliated companies

In the re-allocation period (V7 to V11) treatment completion is defined as:

- non-responder patient receiving 4 infusions of BI 655130 at V7, V8, V9, V10 and continuing in the trial until the last visit (V11) – End of Study/FU1 (Week 32 - 44).
- responder continuing in the trial until the last visit (V10) – Week 28 or until they reach a 50% reduction in EASI score compared to baseline

Early Treatment Discontinuation:

In case the infusion of study drug is permanently discontinued before the whole amount of prepared solution has been administered to the patient, every effort should be made to keep the patient in the trial and complete all of the remaining study visits. If this is not possible, assessments of the primary endpoint V7 (Week16), should be completed or at a minimum an early EoS visit. Please refer to the [Flow Chart](#).

Early Trial Discontinuation:

A patient not having reached the EoS visit within the specified window per protocol (e.g. due to withdrawal of consent, lost to follow-up, death etc.).

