7.8.1 Adverse events

AEs will be coded with the most recent version of MedDRA.

The analyses of AEs will be descriptive in nature. All analyses of AEs will be based on the number of patients with AEs and not on the number of AEs. System organ classes (if applicable) will be sorted according to the standard sort order specified by the EMA, preferred terms (if applicable) will be sorted by total frequency (within system organ class) across all treatment arms.

The analyses of AEs will be performed for double-blind period and for the re-allocation period separately.

For further details on summarization of AE data, please refer to “Analysis and Presentation of Adverse Event data from Clinical Trials” [BI-KMED-BDS-HTG-0066] (7) and “Handling of missing and incomplete AE dates” [BI-KMED-BDS-HTG-0035] (4).

The analysis of AEs will be based on the concept of treatment emergent AEs. If only the start date of an AE is collected (without start time), any AE occurrence on the same day as the first BI 655130 administration will be assigned to the on-treatment phase.

An overall summary of AEs will be presented by treatment.

This overall summary will include summary statistics for the class of other significant AEs (sponsor definition based on ICH E3 (9)) and for the class of AESIs.

The following is considered an AESI in this trial:

- Hepatic injury
- Infusion reactions including anaphylactic reaction
- Severe infections
- Opportunistic and mycobacterium tuberculosis infections

The investigator has to classify on the eCRF whether an observed AE was an AESI or not. Only those AEs that are indicated by the investigator as AESI in the eCRF will be analysed in this category.

Based on the specification provided in ICH E3 (9), the sponsor has defined AEs which are to be classified as ‘other significant’. These will include those non-serious AEs which were reported with ‘action taken = Drug withdrawn’ or ‘action taken = Dose reduced’.

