The frequency of patients with AEs will be summarised by treatment, primary system organ class and preferred term. AEs which were considered by the investigator to be drug related will be summarised separately (secondary safety endpoint of this trial). Separate tables will also be provided for patients with SAEs, patients with drug-related SAEs, patients with AESIs, patients with AE leading to discontinuation of the trial, and patients with other significant AEs (as described previously). AEs will also be summarized by maximum RCTC grade.

A summary of user-defined AE concepts (UDAEC) will be presented by treatment group. The UDAEC are presented in the table below.

Table 7.8.1: 1 Project MEDDRA search criteria for User Defined Adverse Event Concepts

User Defined AE Concepts	Categories
Infusion/Systemic hypersensitivity reactions including anaphylactic reactions	Narrow SMQ “Anaphylactic reaction” Narrow SMQ “Angioedema” Narrow SMQ “Hypersensitivity”
Severe infections (according to RCTC grading)	SOC Infections and infestations of at least severe RCTC grade, by HLGT
Opportunistic infections	MedDRA SMQ Opportunistic Infections (narrow)
Hepatic injuries	See Section 7.8.2
Tuberculosis infections	BIcMQ sub-search 8.2 “Tuberculosis related terms”
Malignant tumours	(SMQ “Malignancies”) (Sub-SMQ “Malignant or unspecified tumours”) Narrow Sub-SMQ “Malignant tumours” Narrow Sub-SMQ “Haematological malignant tumours” Narrow Sub-SMQ “Non-Haematological malignant tumours”
Torsades de pointes	Broad SMQ “Torsades de pointes/QT prolongation”
Malignant skin tumours	(SMQ “Skin neoplasms, malignant and unspecified”) Broad Sub-SMQ “Skin malignant tumours”
Skin melanomas	HLT Skin melanomas (excl. Ocular)
Non-melanoma skin cancer (NMSC)	Broad Sub-BIcMQ “Skin Malignancies excluding melanomas”
Malignancies excluding NMSC	Sub-SMQ “Malignant tumours” excluding broad sub-BIcMQ “Skin Malignancies excluding melanomas”

For disclosure of AE data on ClinicalTrials.gov, the frequency of patients with non-serious AEs occurring with an incidence of greater than 5% (in preferred terms) will be summarised by treatment, primary system organ class and preferred term. The frequency of patients with SAEs will also be summarised.

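### SAP 7.8.1 keys its only discontinuation table for adverse events to leaving the trial, not to stopping trial drug, so it can undercount AE-related drug discontinuation

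*SAP*

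**What the plan says.** SAP 7.8.1 lists the AE tables to be produced. Serious events are covered first: "Separate tables will also be provided for patients with SAEs, patients with drug-related SAEs, patients with AESIs". The same sentence then adds "patients with AE leading to discontinuation of the trial, and patients with other significant AEs (as described previously". No table of AEs leading to discontinuation of trial drug is named.

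The 'other significant' class is defined earlier in 7.8.1 as "non-serious AEs which were reported with ‘action taken = Drug withdrawn’ or ‘action taken = Dose reduced".

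The protocol separates stopping drug from leaving the trial. Section 3.3.4.1 includes adverse events among the medical reasons for stopping treatment and then states: "Even if the trial treatment is discontinued, the patient remains in the trial and, given his/her agreement, will undergo the procedures". Section 6.2.3 defines early treatment discontinuation and early trial discontinuation separately (the latter means not reaching the end-of-study visit). For patients whose infusion is permanently stopped it says that "every effort should be made to keep the patient in the trial and complete all of the remaining study visits".

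Two other parts of the SAP bear on the point. The disposition summary in Section 7 counts patients who stopped study drug early, by reason, overall and in each treatment period. Section 6.6.1 reports the reasons for withdrawal from treatment as recorded on the eCRF.

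**The concern.** An AE that makes a patient stop drug need not end that patient's participation, and this protocol works to ensure that it does not. The better retention works, the fewer drug-stoppers the trial-discontinuation table will show. Read on its own, that table could suggest better tolerability than was observed.

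This matters because Protocol 2.1.1 makes safety and tolerability part of the primary objective and says that they can only be analysed descriptively. The tables are therefore the analysis. When the protocol summarises the earlier palmoplantar pustulosis trial (Section 1.2.3), it reports stopping of drug: "There were 3 AEs leading to discontinuation of trial drug in the placebo arm (14.3"%), with corresponding figures for the two active arms. The present SAP names no AE table for that event.

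**Working it through.** The plan gives no figure to reproduce. The check is to trace where each type of AE-related drug withdrawal would be reported, from the table definitions in SAP 7.8.1 and the disposition summary in SAP 7. It assumes that the eCRF reasons for stopping drug include adverse event; the form is not available.

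| AE that stopped drug | Patient then | Trial-discontinuation table | 'Other significant' table | SAE table | Disposition |
|---|---|---|---|---|---|
| Non-serious (n1) | stays | no | yes, pooled with dose reductions | no | yes, reason only |
| Non-serious (n2) | leaves because of the AE | yes | yes, pooled with dose reductions | no | yes, reason only |
| Serious (n3) | stays | no | no | yes, no stated split by action taken | yes, reason only |
| Serious (n4) | leaves because of the AE | yes | no | yes, no stated split by action taken | yes, reason only |

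1. The count wanted for tolerability is N = n1 + n2 + n3 + n4.
2. Of these, the trial-discontinuation table contains n2 + n4. The share it misses is (n1 + n3)/N. The documents give no split between staying and leaving, so this share can lie anywhere from 0% to 100%.
3. Adding the 'other significant' table does not recover N. Let d be patients with dose reduction only, and e patients who left the trial for an AE that was not a drug withdrawal (for example, a Week 16 responder who was by then off drug). The two tables sum to n1 + 2·n2 + n4 + d + e, which differs from N by n2 + d + e − n3. Non-serious leavers are counted twice, d and e are added, and n3 is absent.
4. Row n3 is the clear gap: these patients are in the SAE table, but in neither AE table keyed to discontinuation.

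For scale only, suppose the rates of the earlier trial (Protocol 1.2.3) applied here. The planned arms are 30 active and 15 placebo.

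- Active: 30 × 1/19 = 1.6 at the 300 mg rate; 30 × 3/19 = 4.7 at the 900 mg rate.
- Placebo: 15 × 3/21 = 2.1, taking the 3 AEs as 3 patients (3/21 = 14.3%, as stated).
- Total: 1.6 + 2.1 = 3.7 to 4.7 + 2.1 = 6.8, or about 4 to 7 of 45. Pooling all arms gives 7/59 = 11.9%, and 0.119 × 45 = 5.3.

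These are rough numbers of patients stopping drug for an AE, not numbers missed. One patient is 1/30 = 3.3 percentage points of the active arm and 1/15 = 6.7 of the placebo arm, so even one case absent from the table is visible.

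**The case against.** The strongest reply is that these patients are not lost from the report. Non-serious drug withdrawals have their own table, named in the same sentence. Serious events are in the SAE tables. Disposition gives drug discontinuation by reason and period, and individual values of all patients are listed. SAP 7.8 and 7.8.1 also defer to sponsor standards that cannot be seen here and may already include the usual table. The phrase may simply be a slip for trial drug. The dose-reduction objection is weak for a fixed-dose regimen with no planned reduction step.

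Most of that stands, and it limits the point to completeness and labelling. It does not close the gap. Disposition carries no event terms, the SAE tables have no stated split by action taken, and a trial-specific SAP that names an event should name the intended one.

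A reader might go further and infer four things that the documents do not support.

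- That most AE-related drug-stoppers would be missed. Retention depends on the patient's agreement, and no share is given.
- That all of roughly 5 patients would fall outside the table. That figure assumes that everyone asked to stay does so, and it carries rates over from another disease and other doses.
- That this is the trial's main tolerability count. SAP 7.5.2.2 designates patients with drug-related AEs as the safety endpoint.
- That results could not be compared with earlier trials of the drug. On the eCRF assumption above, disposition supplies the count of patients who stopped drug for an AE; what it lacks is the event terms.

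**Conclusion.** The point holds as a limited correction. As written, the trial-discontinuation table counts a different event from AE-related drug discontinuation and can undercount the latter. The size of the undercount cannot be derived from the documents. Two gaps are definite on the named tables: a serious AE that stops drug in a patient who stays is in no discontinuation-keyed AE table, and no single table shows all AEs leading to drug withdrawal, serious and non-serious, by event term. The documents give no serious/non-serious split of earlier drug withdrawals, so the first gap has no estimate either.

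The conclusion takes SAP 7.8.1 at its word. If the sponsor's standard AE outputs already include the table, only the wording needs correcting. Efficacy conclusions and the designated safety endpoint are unaffected. The change is worth making because tolerability is a primary objective, the trial is small, and the correction alters a reported count at little cost.

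**What to change.** In SAP 7.8.1, specify a table of patients with AEs leading to discontinuation of trial drug. Define it as action taken = drug withdrawn, whether the event is serious or non-serious, by treatment, system organ class and preferred term. Produce it for the double-blind and re-allocation periods, which 7.8.1 already analyses separately. Keep AEs leading to discontinuation of the trial as a separate, clearly labelled table if wanted. The 'other significant' definition can stay as it is.

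The cost is one table and one sentence. The SAP already uses the action-taken field to define 'other significant' AEs, so no new data should be needed, provided that the field is also completed for serious events.

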7.8.2 Laboratory data

The analyses of laboratory data will be descriptive in nature and will be based on BI standards (8). Note that data from the central Laboratory will be used for all displays described below, unless otherwise specified.

The analyses of safety laboratory parameters will be performed for the double-blind period and re-allocation period separately.

For continuous safety laboratory parameters, normalized values will be derived.

Normalisation means transformation to a standard unit and to a standard reference range. The process of normalisation, handling of repeat values at the same visit for by-visit displays, as well as standard analyses for safety laboratory data are described in the BI guidance for the “Handling, Display and Analysis of Laboratory Data” (8). All analyses considering multiple times of the ULN (as described below) will be based on standardized and not normalized values. For continuous safety laboratory parameters, differences to baseline will be calculated.

Only patients with at least one available post-baseline value will be included in the analysis of an individual laboratory parameter. All individual laboratory data will be listed. Values outside the reference range will be flagged.

Descriptive statistics of laboratory values over time and for the difference from baseline (see Section 6.7) will be based upon normalised values and provided by visit, including summaries of the last value on treatment, the minimum value on treatment and maximum value in the respective period (double-blind or re-allocation).

Laboratory values will be compared to their reference ranges; shift tables will be provided for the number of patients with a specific RCTC grade at baseline versus the grade at the last measurement on treatment, as well as the worst grade on treatment. These analyses will be based on standardized laboratory values.

In addition, box and whiskers plots will be presented for the laboratory parameters.

Potentially clinically significant abnormalities will be identified based on BI standard rules which are based on normalized converted lab values, i.e. using SI units. These rules will be listed in the SDL appendix of the CTR. Frequency tables will summarize the number of patients with potentially clinically significant abnormalities. Patients having an abnormal lab value at baseline will be presented separately. A separate listing will present potentially clinically significant abnormal lab values.

The frequency of patients with AST or ALT elevations $\geq 3\times$ ULN, $\geq 5\times$ ULN, $\geq 10\times$ ULN, and $\geq 20\times$ ULN will be displayed based on standardized laboratory values. To support analyses of liver related adverse drug effects, the frequency of patients with AST and/or ALT $\geq 3\times$ ULN combined with a total bilirubin $\geq 2\times$ ULN in a 30 day period after AST/ALT elevation will be displayed, stratified by alkaline phosphatase $< 2\times$ ULN and $\geq 2\times$ ULN (a patient can potentially be in both alkaline phosphatase strata in case of multiple AST/ALT and bilirubin elevations). The start of the 30 day time span is triggered by each liver enzyme elevation above the defined thresholds. This analysis will be based on standardized laboratory values. A graphical analysis of the ALT and total bilirubin during the on-treatment period will also be performed; the so called eDISH plot. In the graph, for each subject, the peak total bilirubin is presented as a fold increase over the ULN against the peak ALT as a fold increase over the ULN, on a log10 scale. The measurements displayed or total bilirubin and ALT may, or may not, occur on the same date. Two reference lines, $2\times$ ULN for total bilirubin and $3\times$ ULN for ALT, are drawn onto the graph in order to divide the plane into four quadrants. Normal cases are in the lower left quadrant, potential DILI cases are in the upper right quadrant (Hy's Law quadrant), while the lower right quadrant is known as the Temple's corollary range (ALT $\geq 3\times$ ULN and total bilirubin $< 2\times$ ULN).

Clinically relevant findings in laboratory data will be reported as baseline conditions (at screening) or as AEs (during the trial) if judged clinically relevant by the investigator, and will be analysed as such.

7.8.3 Vital signs

The analyses of vital signs (blood pressure, pulse rate, body temperature and body weight) will be descriptive in nature and will be performed for double-blind period and re-allocation period separately.

Descriptive statistics of vital signs over time and for the difference from baseline (see [Section 6.7](#)) will be provided by treatment, including summaries of the last value during the respective period (double-blind or re-allocation), the minimum value during respective period, and the maximum value during respective period (see [Table 6.1: 1](#) for definition of the trial periods/phases).

Clinically relevant findings in vital signs data will be reported as baseline conditions (at screening) or as AEs (during the trial) if judged clinically relevant by the investigator, and will be analysed as such.

7.8.4 ECG

Abnormal findings in 12-lead ECG will be reported as baseline conditions (at screening) or as AEs (during the trial) if judged clinically relevant by the investigator, and will be analysed as such.

No separate listing or analysis of ECG data will be prepared.

7.8.5 Others

7.8.5.1 Infusion reactions including anaphylactic reaction

Infusion reactions will be summarized overall, with the frequency and percentage of patients who experienced any infusion reaction, both overall and specifying anaphylactic reaction as part of the table presenting patients with adverse events of special interest (AESI).

7.8.5.2 Immunogenicity

The frequency and percentage of patients with ADAs to BI 655130 will be presented by treatment by visit and overall, if sufficient data is available.

Further exploratory assessments of the ADA data (e.g. relationship between ADA and PK) might be performed once data is available and these will be described, if done, in the CTR.

[figure not shown]
7.8.5.3 Handling of DMC Analyses

A partially external DMC, independent of the trial and project teams, was set-up on project level to review all available safety data as well as selected efficacy data in an unblinded manner at regular intervals following first-patient-in. A separate DMC SAP which describes

the analyses required for assessment by the DMC was produced and finalized prior to first patient randomised into the trial. Further details were provided in a DMC charter.

